10.9.2 Concomitant Medication Missing or Partial End Dates

Medications with partial end dates will only be considered prior if the partial end date indicates that the medication was stopped prior to first study vaccination. All other medications with missing or partial end dates will be considered concomitant.

10.9.3 HBV History Missing or Partial Dates

If the date of first diagnosis or start date of current anti-viral therapy is partial, the following rules will take effect:

- Missing day, but month and year are present: the day will be imputed as the 15th day of the month, or date of informed consent, whichever is earlier
- Missing day and month, but year is present: the day and month will be imputed as the 1st July of the year, or date of informed consent, which is earlier
- Missing day, month, and year: no imputations will occur and the participant will be excluded from all summaries related to time since HBV diagnosis and duration of current anti-viral therapy

10.10 Multiple Assessments at a Time Point

If a participant has more than one assessment taken at the same time point (e.g. laboratory results, vital signs), for baseline the latest date and time prior to first study vaccination is used. For post-baseline visits, the worst clinical value in the direction of the toxicity presented will be used in the analysis for that time point. All values will be listed.

In cases where solicited AE or daily temperature records are recorded on both the eDiary and CRF with the same date/time, for the primary analysis we will select the CRF record to use. If the solicited AE or daily temperature record was only collected on either the eDiary or the CRF, then all records will be considered for the primary analysis.

For a sensitivity analysis, all records including records identified as duplicates will be used. All records will be listed.

11.0 Interim Analyses

11.1 Interim Analyses

An interim analysis will be performed for all data collected when at least 20 participants have been enrolled (with four participants randomised to Group 3 and Group 4) and followed for 3 months.

As the study is open-label, no unblinding needs to occur, and as such the interim analyses will be performed by the PRA team. The results of the interim analysis will be used to determine the development plans for the Phase 3 study.

The interim analysis will contain a subset of the CSR outputs as listed in Section 16.0. The details of how the analyses will be performed are specified within each section of the statistical methods part of this SAP.

11.2 Safety Monitoring Committee

A safety monitoring committee (SMC) will be appointed to review the study data throughout the study and at specific time points.

11.3 Data Monitoring Committee

An independent Data Monitoring Committee (DMC) will be utilised for this study. Ad hoc meetings of the DMC may be called at the discretion of the SMC or if any of the study stopping or holding rules are met.

A DMC charter including a detailed description will be prepared. A subset of CSR outputs as listed in Section 16.0 will be produced for review at these meetings.

12.0 Statistical Methods

All statistical analyses will use SAS version 9.4 or higher.

Unless otherwise noted, categorical variables will be summarised using counts and percentages. Percentages will be rounded to one decimal place, except 100% which will be displayed without any decimal places, and percentages will not be displayed for zero counts. Denominators used for percentages will be the population N unless otherwise specified.

For tables with a percent cut-off, the cut-off is applied to the percentage before rounding.

Continuous variables will be summarised using the number of observations (n), mean, Standard Deviation (SD), median, Q1, Q3, minimum, and maximum. Summaries of HBsAg will present the number of observations (n), geometric mean (GM), geometric standard deviation (GSD), median, minimum, and maximum. The minimum and maximum values will be displayed to the same level of precision as the raw data, the mean, GM, median, Q1, and Q3 to a further decimal place and the SD and GSD to two additional decimal places. All values will be presented to a maximum 4 decimal places.

Where relevant, estimates will be presented with 95% two-sided confidence intervals using the same number of decimal places as the parameter estimate. P-values ≥ 0.001 will be reported to three decimal places; p-values less than 0.001 will be reported as <0.001 .

Participants will be summarised by treatment group (Group 1, 2, 3, or 4) and in addition by Total for demography and safety tables. In general, all categories specified in the eCRF will be presented in summary tables.

Unless otherwise specified, all data collected during the study will be presented in the participant data listings by treatment group, study site, and participant ID.

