9.2.3 Safety Analysis Set

The safety analysis set is defined as all participants who received at least one vaccination. Participants will be presented according to the vaccination regimen actually received as defined in Table 2. This will be the analysis set for all safety analyses.

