10.0 Conventions and Derivations

10.1 Treatment Groups

In the outputs, the treatment groups will be labelled as Group 1, Group 2, Group 3 and Group 4, rather than the full description of the first and second vaccinations, in order to conserve space. The definitions of these 4 groups are described in Table 1.

Table 1 Treatment Groups

Treatment Group	1 st Vaccination	2 nd Vaccination
Group 1	MVA-HBV 1 x 10 ⁸ pfu	MVA-HBV 1 x 10 ⁸ pfu
Group 2	ChAdOx1-HBV 2.5 x 10 ¹⁰ vp	MVA-HBV 1 x 10 ⁸ pfu
Group 3	ChAdOx1-HBV 2.5 x 10 ¹⁰ vp	MVA-HBV 1 x 10 ⁸ pfu + Nivolumab 0.3 mg/kg
Group 4	ChAdOx1-HBV 2.5 x 10 ¹⁰ vp + Nivolumab 0.3 mg/kg	MVA-HBV 1 x 10 ⁸ pfu + Nivolumab 0.3 mg/kg

For the safety analysis, the actual treatment groupings are assigned as follows:

- Group 1 = MVA-HBV in 1st vaccination
- Group 2 = ChAdOx1-HBV in 1st vaccination, No Nivolumab in 2nd vaccination
- Group 3 = ChAdOx1-HBV in 1st vaccination, Nivolumab in 2nd vaccination
- Group 4 = ChAdOx1-HBV + Nivolumab in 1st vaccination

The possible combinations of treatments at the first and second vaccinations and the resulting actual treatment group are described in Table 2.

Table 2 Actual Treatment Groups

Randomisation	Actual 1 st Vaccination Given	Actual 2 nd Vaccination Given	Treatment Group Assigned for the Safety Analysis
Group 1	MVA-HBV	MVA-HBV	Group 1
Group 2	ChAdOx1-HBV	MVA-HBV	Group 2

Randomisation	Actual 1 st Vaccination Given	Actual 2 nd Vaccination Given	Treatment Group Assigned for the Safety Analysis
Group 3	ChAdOx1-HBV	MVA-HBV + Nivolumab	Group 3
Group 4	ChAdOx1-HBV + Nivolumab	MVA-HBV + Nivolumab	Group 4
Group 1	MVA-HBV	No vaccination given	Group 1
Group 2	ChAdOx1-HBV	No vaccination given	Group 2
Group 3	ChAdOx1-HBV	No vaccination given	Group 2
Group 4	ChAdOx1-HBV + Nivolumab	MVA-HBV (Nivolumab not given)	Group 4
Group 4	ChAdOx1-HBV + Nivolumab	No vaccination given	Group 4
Group 3	ChAdOx1-HBV	MVA-HBV (Nivolumab not given)	Group 2
Group 4	ChAdOx1-HBV (Nivolumab not given)	MVA-HBV + Nivolumab	Group 3
Group 4	ChAdOx1-HBV (Nivolumab not given)	MVA-HBV (Nivolumab not given)	Group 2
Group 4	ChAdOx1-HBV (Nivolumab not given)	No vaccination given	Group 2

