12.7 Safety Analyses

All safety analyses will be presented using the Safety analysis set.

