12.7.1 Primary Endpoints

The primary endpoints are:

- Safety and reactogenicity of the vaccine(s): incidence of AEs, SAEs, \geq Grade 3 study vaccine-related AEs within 4 weeks of vaccination
- Safety of the vaccines with nivolumab: incidence of AEs, SAEs, \geq Grade 3 AEs within 4 weeks of dosing
- Incidence of AESI
- Number and proportion of participants reporting TEAEs within each treatment group
- Number and proportion of participants within each treatment group with potentially clinically significant laboratory values and vital signs within each treatment group
- Change from baseline in laboratory tests and vital sign measurements to each time point of collection

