12.7.1.1 Adverse Events

The number and percentage of participants reporting each adverse event, including the number of events, will be summarised by SOC and PT coded according to the MedDRA dictionary. Participants are only counted once within each SOC and PT. AEs will be sorted by decreasing frequency within each SOC and PT according to the overall treatment group.

In addition, summaries will be provided for the subset of AEs, SAEs, and Grade 3 or greater AEs that occurred within 28 days of first vaccination and second vaccination (vaccination day + 27 days) separately.

AESI will also be tabulated by PT for all events occurring during the study.

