12.7.2.2 Solicited Adverse Events

For each solicited symptom (grouped by local symptoms and systemic symptoms), the number and percentage of participants reporting an event will be summarised by vaccination (first vaccination, second vaccination) and overall.

For participants experiencing a solicited symptom (i.e. reporting a severity Grade 1 or higher), an additional summary of solicited symptoms by maximum severity after each vaccination (first vaccination, second vaccination) and overall will be presented.

Percentages for both analyses are based on the number of participants reporting the severity of any solicited symptom on any day within the 7-day reactogenicity period following each vaccination (as defined in Section 10.5.5).

Both analyses will be presented for the primary analysis and repeated for the sensitivity analysis (as defined in Section 10.10).

Solicited AEs, local and system reactogenicity, and diary body temperature will be listed separately. A combined listing including solicited symptoms from both the eDiary and CRF for the 7-day reactogenicity period will also be presented.

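### Adverse-event percentages for the second-vaccination window default to the whole safety set, which dilutes Groups 1, 2 and 4 and the Total column if anyone misses dose 2, and skews the comparison of Group 2 with Group 3

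*SAP*

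**What the plan says.** The general rule in SAP 12.0 is "Denominators used for percentages will be the population N unless otherwise specified". SAP 12.7 adds: "All safety analyses will be presented using the Safety analysis set". SAP 9.2.3 sets the entry condition: "The safety analysis set is defined as all participants who received at least one vaccination". A second dose is not required.

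SAP 12.7.1.1 asks for subset summaries of AEs, SAEs and Grade 3 or higher AEs "within 28 days of first vaccination and second vaccination (vaccination day + 27 days) separately". The overall table in SAP 12.7.2.1 has matching second-vaccination rows for AEs and Grade 3 or higher AEs. Neither section states a denominator, so the default applies. These summaries serve the primary safety endpoints, which concern incidence in the 4 weeks after vaccination or dosing (SAP 12.7.1).

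The plan foresees participants with one dose only:

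- SAP Table 2 has rows marked "No vaccination given" at the second vaccination for every randomised group.
- SAP 12.5 tabulates how many received only the first dose.
- Protocol 3.1.4 and 4.3.1.2 provide for withdrawal from further vaccination.
- Protocol 5.7 provides for replacing participants who discontinue after vaccination. The participant who was replaced has still had one vaccination and stays in the safety set.

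Solicited AEs are treated differently. SAP 12.7.2.2 states: "Percentages for both analyses are based on the number of participants reporting the severity of any solicited symptom on any day", with the days limited to the 7-day period after each vaccination.

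**The concern.** A percentage tied to a window after dose 2 should rest on people who entered that window. Someone who stopped after dose 1 cannot have an event there, so including that person can only pull the percentage down. The more participants stop after dose 1, the lower the second-dose percentage looks in a column that retains them.

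Two features make this more than a matter of layout. The summaries feed primary endpoints, and the groups are small (9 to 16), so one participant shifts a percentage visibly. The retained participants are also spread unevenly across columns. SAP Table 2 assigns safety groups by treatment received, and that rule empties Group 3 of one-dose participants and places them in Group 2. Groups 2 and 3 are the two groups still recruiting under protocol version 6.0. Comparing them contrasts the MVA-HBV boost without and with nivolumab.

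**Working it through.** **Inputs**
- Group 1 has n = 10 and Group 4 has n = 9 (SAP 8.1). Groups 2 and 3 are planned at 16 each (protocol 3.2).
- k, the number in a safety-set column without dose 2, is not given. The range k = 0 to 3 is assumed.

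**The plan's own figure.** SAP 8.1 gives an 80% chance of seeing an event of 10% incidence with 16 participants. The check is 1 − 0.9^16 = 0.815, so the figure reproduces. It depends on the number exposed: with 14 dosed, 1 − 0.9^14 = 0.771.

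**Who stays in which column (SAP 10.1 and Table 2)**
- Groups 1 and 4 are defined by the first vaccination alone, so one-dose participants remain in them.
- Group 2 keeps its own one-dose participants. It also receives those randomised to Group 3, and those randomised to Group 4 who had no nivolumab at dose 1, when no second vaccination was given.
- Group 3 requires nivolumab at the second vaccination. Everyone in it had dose 2, so k = 0 by construction.
- The Total column, which SAP 12.0 requires for safety tables, contains every one-dose participant.

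**Size of the dilution.** With x participants having an event, the plan reports x/N. The rate among those dosed is x/(N − k). The ratio is (N − k)/N, so the relative understatement is k/N.

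| Column | N | k = 1 | k = 2 | k = 3 |
|---|---|---|---|---|
| Group 1 | 10 | 10.0% | 20.0% | 30.0% |
| Group 4 | 9 | 11.1% | 22.2% | 33.3% |
| Group 2 (own participants) | 16 | 6.3% | 12.5% | 18.8% |
| Group 3 | any | not possible | not possible | not possible |

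If the planned and closed sizes sum to 10 + 16 + 16 + 9 = 51, the Total column loses 1/51 = 2.0% for one missed dose and 2/51 = 3.9% for two.

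In percentage terms, a 50% rate among those dosed with k = 2 is reported as:
- 0.50 × 8/10 = 40.0% in Group 1
- 0.50 × 7/9 = 38.9% in Group 4
- 0.50 × 14/16 = 43.8% at N = 16

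**Effect on Group 2 against Group 3 (assumed counts).** Randomise 16 to each group. Two participants in Group 3 miss dose 2, and all of Group 2 receive it. The rate among those dosed is 50% in both groups.
- Table 2 gives safety Group 2 N = 16 + 2 = 18, with 16 dosed and 8 events. The reported rate is 8/18 = 44.4%.
- Safety Group 3 has N = 16 − 2 = 14, all dosed, with 7 events. The reported rate is 7/14 = 50.0%.
- The apparent difference of 5.6 points comes from the denominator alone. With dose-2 recipients as denominator, the rates are 8/16 = 50.0% and 7/14 = 50.0%.

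If only one Group 3 participant misses dose 2, Group 2 has N = 17 and the understatement is 1/17 = 5.9%.

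**The case against.** **The raw material is reported.** Event counts appear beside the percentages. The exposure table gives the numbers with both doses and with the first dose only, on the same safety set (SAP 12.5). The AE summaries are descriptive, with no test attached. A careful reader could therefore recompute the rate. This stands and lowers the severity, but the percentage printed for a primary endpoint would still be the diluted one.

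**Both rates are legitimate.** Events over everyone who started the regimen is a real quantity. Events over dose-2 recipients is conditional on having continued past dose 1, so it carries selection of its own, and a comparison of dose 1 with dose 2 is not clean either way. This also stands. However, the plan applies the default across columns that differ in whether they can contain one-dose participants at all, so Group 2 and Group 3 would not be reporting the same quantity.

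**The effect is small against sampling error.** With assumed counts of 5 events, 17 in the safety set and 14 dosed, 5/17 is 29.4% (exact 95% CI 10.3% to 56.0%) and 5/14 is 35.7% (12.8% to 64.9%). The intervals overlap almost entirely. That is true, but sampling error does not justify a denominator that includes people not at risk.

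**Stronger readings that the documents do not support**
- A reader might infer that the second-dose rate for the main nivolumab arm, Group 3, is understated. It is not: SAP Table 2 leaves no one-dose participant there. For columns that include nivolumab at dose 2, direct dilution is confined to Group 4, which is closed, and to the Total column.
- A reader might infer that any regimen poorly tolerated at dose 1 will look safer at dose 2. For Group 3 the relative effect runs the other way: its one-dose participants lower Group 2's percentage, so Group 3 looks worse by comparison.
- A reader might infer that solicited reactions share the problem. They have a denominator tied to reporting after each vaccination. It counts people with reported severity data, so it is not purely an exposure count, but it does not retain people with no second-dose reports.

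**Conclusion.** The concern holds in a limited form. By the SAP's own default, second-vaccination percentages for unsolicited AEs, SAEs and Grade 3 or higher AEs include safety-set participants who were never in that window. The understatement is k/N, and it applies to Groups 1, 2 and 4 and the Total column. One missed second dose costs 10.0%, 11.1% and 6.3% of the rate in Groups 1, 4 and 2 respectively, at the sizes given above. Group 3 is unaffected in its own column, but the reassignment of its one-dose participants distorts the comparison of Group 2 with Group 3.

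All of this is conditional. It requires at least one missed second dose and at least one event in the column, and the documents give no count of missed doses. A reader should not conclude that any rate is in fact understated: if everyone received dose 2, nothing changes. Because the correct figure can be recovered from planned outputs and the analyses are descriptive, this is a modest point that is worth correcting.

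**What to change.** Add one sentence to SAP 12.7.1.1 and to SAP 12.7.2.1: for events in the 28 days after the second vaccination, percentages use the safety-set participants in that column who received the second vaccination, and that n is shown in the column or row header. Keep population N for the first-vaccination window and for whole-study rows.

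This corrects Groups 1, 2 and 4 and the Total column, leaves Group 3 unchanged, and puts Groups 2 and 3 on the same footing without altering the safety-group assignment in Table 2. The count is already produced for the exposure table in SAP 12.5, so the work is one sentence per section and a header n in the affected tables. The price is that some second-dose percentages become slightly less favourable. They must also be read as conditional on having continued to dose 2, which a table footnote can say.

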## 2 STUDY OBJECTIVES AND ENDPOINTS

### Objectives

### Endpoints

#### Primary Objectives

- Determine the safety and reactogenicity of the following in participants with CHB infection and virally suppressed with oral antiviral medication:
  - MVA-HBV vaccine
  - ChAdOx1-HBV plus MVA vaccines
  - ChAdOx1-HBV plus MVA vaccines and nivolumab

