7.0 Study Objectives

Note (*): While the protocol's primary and secondary objectives as written do not explicitly differentiate between ChAdOx1-HBV plus MVA-HBV vaccines with and without nivolumab (i.e., Group 3 and Group 4), the intent was to evaluate the safety, reactogenicity, and immunogenicity for each treatment group. Therefore, this SAP has been developed to evaluate each group's effect on these objectives.

Note (**): While the protocol's secondary objective as written does not explicitly reference the MVA-HBV-only group (i.e., Group 1), the intent was to evaluate each treatment group's effect on Hepatitis B markers. Therefore, this SAP has been developed to evaluate each group's effect on these markers.

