7.1 Primary Objectives

- Determine the safety and reactogenicity of the following in participants with Chronic Hepatitis B Virus (CHB) infection and virally suppressed with oral antiviral medication:
 - MVA-HBV vaccine

- ChAdOx1-HBV plus MVA-HBV vaccines
- ChAdOx1-HBV plus MVA-HBV vaccines and nivolumab*

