8.1 Sample Size Considerations

The sample size of 16 participants per treatment group was originally chosen to assess the variability in both immunologic responses, as well as the potential change in HBsAg. With 16 participants, the trial also has an 80% chance to detect any severe or serious adverse event that would occur at a 10% incidence.

Following the interim analysis, enrolment into Groups 1 and 4 ceased (with n=10 and 9, respectively), and enrolment continued for Groups 2 and 3 in a 1:1 randomisation allocation.

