12.7.2 Other Safety Endpoints

12.7.2.1 Other Adverse Events

An overall summary of treatment-emergent adverse events, including the number of events reported, will be provided for:

- Any AEs
- Any AEs within 28 days of first vaccination
- Any AEs within 28 days of second vaccination
- Any grade 3 or greater AEs within 28 days of first vaccination
- Any grade 3 or greater AEs within 28 days of second vaccination
- Any AEs related to study vaccines
- Any AEs related to nivolumab

- Any AEs related to study vaccines or nivolumab
- Any grade 3 or greater AEs related to study vaccines
- Any grade 3 or greater AEs related to nivolumab
- Any grade 3 or greater AEs related to study vaccines or nivolumab
- Any AEs with outcome of death
- Any serious AEs
- Any serious AEs related to study vaccines
- Any serious AEs related to nivolumab
- Any serious AEs related to study vaccines or nivolumab
- Any AEs leading to discontinuation of study vaccines
- Any AEs leading to discontinuation of nivolumab
- Any AEs leading to discontinuation of study vaccines or nivolumab
- Any AEs of special interest

Deaths will be identified using the AE eCRF.

In addition, individual summary tables by SOC and PT will be provided for each category (with the exception of any AEs with outcome of death) in the overall TEAE table and presented similarly to the primary endpoint in Section 12.7.1.1. A by-participant summary of all TEAEs leading to death, serious TEAEs, and TEAEs leading to discontinuation of study vaccines or nivolumab will be produced.

AEs leading to discontinuation of study vaccines or nivolumab are defined as any AE with Action Taken with Study Vaccines = 'Drug Withdrawn' or Action Taken with Nivolumab = 'Permanently Discontinue' recorded on the Unsolicited AEs eCRF.

TEAEs will be further summarised by maximum severity (grade 1, grade 2, grade 3, grade 4, grade 5) within each SOC and PT. Participants with multiple events within a particular SOC or PT will be counted under the category of their most severe event within that SOC or PT.

Non-treatment-emergent AEs will be presented by SOC and PT.

All adverse events (including non-treatment-emergent events) recorded on the eCRF will be listed separately.

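### No pooled safety estimate is planned for nivolumab-exposed participants, and the Total column for nivolumab-related AEs is about half unexposed

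*SAP*

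**What the plan says.** The primary objective lists the nivolumab regimens as a single item: "ChAdOx1-HBV plus MVA vaccines and nivolumab" in Protocol 2, and "ChAdOx1-HBV plus MVA-HBV vaccines and nivolumab" in SAP 7.1. The matching primary endpoint in SAP 12.7.1 is also one item: "Safety of the vaccines with nivolumab: incidence of AEs, SAEs" and Grade 3 or higher AEs in the four weeks after dosing. A note in SAP 7.0 explains how the single item is to be read: "the intent was to evaluate the safety, reactogenicity, and immunogenicity for each treatment group".

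SAP 12.0 sets the layout: "Participants will be summarised by treatment group (Group 1, 2, 3, or 4) and in addition by Total for demography and safety tables". It also sets the denominator: "Denominators used for percentages will be the population N unless otherwise specified".

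SAP 12.7.1.1 tabulates AEs, SAEs and Grade 3 or higher AEs in the 28 days after each vaccination, with separate tables for the first and the second. It tabulates AESIs over the whole study.

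The overview in SAP 12.7.2.1, under Other Safety Endpoints, adds rows by relationship, such as "Any grade 3 or greater AEs related to nivolumab", with corresponding rows for all AEs and serious AEs and a row for discontinuation of nivolumab. Each also gets its own SOC/PT table. No special denominator is given for any of them. The Grade 3 or greater nivolumab-related table (14.3.2.14) is also on the DMC and interim output list in SAP 16.0.

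**The concern.** The plan asks one question about the vaccines given with nivolumab but has no column that holds everyone who received it. The answer comes in two small pieces, and Group 4 closed at 9 participants.

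The only printed figure that spans both exposed groups is the Total. In the nivolumab-related and nivolumab-discontinuation rows its denominator includes Groups 1 and 2, who are given no nivolumab. A reader who takes the Total as the overall nivolumab-related rate would read a figure about half the size it should be, in a study where safety with nivolumab is a primary question.

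**Working it through.** **Inputs**

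- Groups 1 and 4: SAP 8.1 reports that "enrolment into Groups 1 and 4 ceased (with n=10 and 9, respectively" in number.
- Groups 2 and 3: planned n=16 each (Protocol 3.2 and Table 1). Their final sizes are not in the documents.
- Exposure as treated (SAP 10.1, Table 2): Group 3 requires nivolumab at the second vaccination and Group 4 requires it at the first. Anyone randomised to Group 3 or 4 who received none is counted in Group 2. As-treated Groups 3 and 4 together are therefore the exposed participants.

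**The plan's own figure.** SAP 8.1 gives an 80% chance that 16 participants reveal an event of 10% incidence. The formula 1 − 0.9^n gives 1 − 0.9^16 = 0.815, which agrees.

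**Share of the Total that is exposed**

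- Planned: (16 + 9)/(10 + 16 + 16 + 9) = 25/51 = 49.0%; unexposed 26/51 = 51.0%.
- Group 4 at 8 or 10 (the range in Protocol Table 1): 24/50 = 48.0% or 26/52 = 50.0%.
- Groups 2 and 3 both at 14 or both at 18: 23/47 = 48.9% or 27/55 = 49.1%.
- Only Group 2 at 18, or only Group 3 at 18: 25/53 = 47.2% or 27/53 = 50.9%.

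In all these cases the share stays near one half.

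**Effect on a nivolumab-related row**, assuming no such event is recorded in Groups 1 and 2:

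| Events (Group 3 + Group 4) | Group 3 | Group 4 | Exposed | Total as planned |
|---|---|---|---|---|
| 2 + 1 | 2/16 = 12.5% | 1/9 = 11.1% | 3/25 = 12.0% | 3/51 = 5.9% |
| 3 + 2 | 3/16 = 18.8% | 2/9 = 22.2% | 5/25 = 20.0% | 5/51 = 9.8% |

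**What pooling would add**, if the two groups share one event rate. The upper limit is the exact two-sided 95% limit with no events, 1 − 0.025^(1/n):

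| n | Chance of at least one event at 10% incidence | Upper limit with no events |
|---|---|---|
| 9 (Group 4) | 61.3% | 33.6% |
| 16 (Group 3) | 81.5% | 20.6% |
| 25 (pooled) | 92.8% | 13.7% |

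**A second route to error.** SAP 10.5.2 treats a missing relationship to nivolumab as related and makes no exception for participants never given it. A blank field in Group 1 or 2 could therefore become a nivolumab-related AE in an unexposed person. The documents do not say how the eCRF handles this field in those groups.

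**The case against.** A reader might infer that the primary endpoint gets no estimate at all in nivolumab-exposed participants, or that its rates are halved. The documents support neither reading.

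- The as-treated Group 3 and Group 4 columns contain only exposed participants. Each gives an undiluted incidence, including in the 28 days after the second vaccination.
- The primary endpoint counts AEs, SAEs and Grade 3 or higher AEs whatever their relationship to nivolumab. Groups 1 and 2 can have those events, so the Total in the primary tables is an ordinary all-participant rate. The dilution arises only in the relationship and discontinuation rows, which the SAP places under Other Safety Endpoints.
- Analysis by group is an open choice, stated in SAP 7.0, and not an oversight.

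There is also a case against pooling. Groups 3 and 4 differ by design in the timing and number of infusions, and timing of PD-1 blockade is itself a secondary objective. Protocol 3.2 reports mean log10 HBsAg changes of −1.04 and −0.13 in these groups at Month 3. A common event rate is an assumption. The Total is never named as the nivolumab estimate, no holding rule in Protocol 3.1.3 uses it, and a reader can add two columns by hand.

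All of this stands, and it limits the point to presentation. It justifies keeping the group columns. It does not justify printing a nivolumab-related percentage with a denominator that is half unexposed.

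**Conclusion.** The point holds as a cheap improvement. Safety with nivolumab is estimated in Group 3 and Group 4 separately, as intended, and no pooled exposed estimate is planned. In the nivolumab-related and nivolumab-discontinuation rows, the Total percentage is about 49% of the rate among the exposed. This rests on the planned sizes for Groups 2 and 3 and on no nivolumab-related AE being recorded in Groups 1 and 2.

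A pooled column would lower the zero-event upper limit to 13.7%, from 20.6% in Group 3 and 33.6% in Group 4, but only if the two groups have similar event rates. No primary incidence is wrong or missing as the plan stands.

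**What to change.** 1. In SAP 12.7.2.1, for the rows on AEs, Grade 3 or greater AEs and serious AEs related to nivolumab, for the row on discontinuation of nivolumab, and for their SOC/PT tables: print *not applicable* for Groups 1 and 2, and replace Total by *Any nivolumab*, with participants given at least one infusion as denominator. This also stops the missing-relationship rule in 10.5.2 from creating nivolumab-related events in unexposed participants. Rows that combine study vaccines or nivolumab can keep their Total, because Groups 1 and 2 can have those events.
2. In SAP 12.7.1.1, add a supplementary column *Any nivolumab (as-treated Groups 3+4)* in two places:
   - In the tables for the 28 days after the second vaccination, count only events in that window and include only participants who received nivolumab at that vaccination. SAP Table 2 keeps in Group 4 some who did not.
   - In the AESI table, count events from each participant's first infusion, in that column only. Group 3 has no nivolumab between Day 0 and Day 28.
3. Keep all existing group columns. Footnote that the pooled column mixes one and two infusions and assumes similar event rates.

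The cost is a few lines of SAP text, one extra column in a small set of tables and a footnote. No new data or analysis set is needed. If the database is already locked, Protocol 10.2 provides the route: document and justify the change in the clinical study report.
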